## Rank Analysis of Variance (ANOVA)

Number of new or newly-enlarged T2 lesions will be analyzed using the rank ANOVA adjusted for treatment and region on the full analysis set. Unlike Rank ANCOVA where continuous covariates exist, the PROC RANK and PROC REG steps are not necessary. The van Elteren's test will be used for treatment comparisons. The van Elteren's test is a rank based test and can be implemented in PROC

FREQ with options CMH2 and score equal to MODRIDIT. The van Elteren's test statistic corresponds to the row mean scores statistic labeled "Row Mean Scores Differ" in the CMH output.

Below is an example of the SAS codes used to perform this rank ANOVA. The independent variables and covariates in the model may change per analysis defined in this document.

```
************
```

## 12.1.1.3 Logistic regression for proportion variables

The other secondary/other efficacy variables ( , proportion of subjects free of new or newly enlarging T2 lesions, proportion of subjects free of Gd + lesions, proportion of subjects free of new T1 lesion) will be analyzed using the logistic regression on the full analysis set. All 3 treatment groups will be used in the model.

Logistic regression is a model for prediction of the probability of occurrence of an event. It can be used to analyze the dichotomous response data while adjusting for one or more covariates. Usually, Logistic regression analyzes binomially distributed data of form

$$Y_i \sim B(n_i, p_i)$$
, for  $i = 1, \dots, n$ .

The logits of the unknown binomial probabilities (i.e., the logarithms of the odds) are modeled as a linear function of the  $X_i$ .

$$\log(\frac{p_i}{1-p_i}) = \beta_0 + \beta_1 x_{1,i} + \dots + \beta_k x_{k,i}.$$

run;

Below is an example of the SAS codes used to perform the analysis of the LOGISTIC regression. The independent variables and covariates in the model may change per analysis defined in this document.

For this study, proc logistic is performed including all 3 treatment levels with the contrast specifying 2 levels.

#### 12.1.1.4 Survival analysis for time to event variables

Log-rank test will be used to compare the survival distributions of two treatment groups for secondary efficacy time to event variables, analyses will be performed on the full analysis set.

The logrank test is a hypothesis test to compare the survival distributions of two samples. It is a nonparametric test and appropriate to use when the data are right skewed and censored (technically, the censoring must be non-informative). It is constructed by computing the observed

and expected number of events in one of the groups at each observed event time and then adding these to obtain an overall summary across all time points where there is an event.

Cox proportional hazards model is to estimate the effect parameter(s) without any consideration of the hazard function assuming the proportional hazards assumption holds. The proportional hazards assumption is the assumption that effect parameters multiply hazard: for example, if taking drug X halves your hazard at time 0, it also halves your hazard at time 1, or time 0.5, or time t for any value of t. The effect parameter(s) estimated by any proportional hazards model can be reported as hazard ratios.

Below is an example of the SAS codes used to perform the Log-rank test with Kaplan-Meier Method and the Cox proportional hazards model. The independent variables and covariates in the model may change per analysis defined in this document.

\*\*\*\*\*\*\*\*\*\*\*\*\*\*\*\*\*\*

```
* SAS Codes: LOG-RANK test with Kaplan-Meier Method
* Variables in the model:
* reltm =
* trt = treatment group code
* relcens = censor flag (1=censored, 0=not censored)
*********************
proc lifetest data=eff method=km;
    where trt in ('A','B');
    time reltm*relcens(1);
    strata trt;
run;
*****************
* SAS Codes: Cox's regression model
* Variables in the model:
* reltm =
* trt = treatment group code
* reg1a = region code
* n2 = number of relapses in previous year
* bledss = baseline EDSS
```

\* relcens = censor flag (1=censored, 0=not censored)

\* more covariates could be added as needed

```
**********************
***include all 3 treatment arms data in one model fitting***
proc phreq data=datain nosummary;
  class trt regla
  model reltm*relcens(1)=trt n2 bledss reg1a (more covariates as needed)/rl
ties=exact;
  contrast "A vs C" trt 1 0 -1/estimate=exp;
  contrast "B vs C" trt 0 1 -1/estimate=exp;
  contrast "A vs B" trt 1 -1 0/estimate=exp;
  ods output parameterestimates=pest;
  ods output contrastestimate=est;
run;
**Note that data set pest contains Hazard ratio estimates from model
statement where only A vs C and B vs C are available. If parameter='trt',
then SELECT probchisq hazardratio hrlowercl hruppercl for results;
**However, data set est contains Hazard ratio estimates from contrast
```

## 12.1.1.4.1 Estimation of 95% confidence intervals

names: estimate lowerlimit upperlimit probchisq);

Approximate 95% confidence intervals will be generated for several estimates: (1) at selected time-points, the (Kaplan and Meier 1958) estimates of the proportion of subjects experiencing a specific event, (2) at selected time-points, the between-treatment group difference in Kaplan-Meier estimates of the proportion of subjects experiencing a specific event, (3) for certain study periods, the between-treatment group difference in the proportion of subjects experiencing a specific event, and (4) at selected time-points, the between-treatment group difference in means. Details of such confidence intervals are displayed in Table 5-1.

statement where all 3 pairwise comparisons are available (result variable

**Table 12-1 Confidence Interval calculations** 

	Approximate Confidence Interval (CI)	Lower Limit	Upper Limit		
1	x% CI for the Kaplan-Meier estimate KM	KM - c x *SE	$KM + c_x^*SE$		
	Notation: SE = estimated standard error of KM;				
	estimation of standard error uses Greenwood's formula,				
	$c_x = \Phi^{-1}(\frac{1}{2} + \frac{x}{200})$ , where $\Phi$ is the normal distribution function.				
2	x% CI for the difference in Kaplan-Meier	$KM_2$ - $KM_1$ - $c_x$ * $SE_d$	$KM_2$ - $KM_1 + c_x*SE_d$		
	estimates KM 2 -KM 1				
1					

```
Notation: KM_i = Kaplan-Meier estimate for group i = 1,2, SE_d = \sqrt{(SE_1^2 + SE_2^2)}, \text{ where } SE_i^2 = \text{estimated standard error of } KM_i, i = 1,2; estimation of standard error uses Greenwood's formula, c_x = \Phi^{-1}(\frac{1}{2} + \frac{x}{200}), \text{ where } \Phi \text{ is the normal distribution function.} Examples: for x = 95, c_x = \Phi^{-1}(0.975) = 1.95996; for x = 97.5, c_x = \Phi^{-1}(0.9875) = 2.24140
```

## 12.1.1.5 Between-treatment group comparisons for other efficacy variables

Generally, non-stratified, non-parametrical tests will be used to perform between-treatment group comparisons on MS confirmed relapse characteristics and change from baseline in disability, MRI variables (Gd + T1 lesion count, T2 lesion volume, Gd + lesion volume, T1 hypointense lesion volume, and changes from baseline in T2 lesion volume and Gd + lesion volume, percentage change from baseline in brain volume). Tests applied will be the rank ANCOVA. For a small number of comparisons, Wilcoxon rank-sum test for continuous variables will be utilized; Fisher's exact test will be used for categorical variables; for variables with more than five categories it will be replaced with the chi-square test. Wilcoxon rank-sum test is also used for comparison between the treatment groups

Below is an example of the SAS codes used to perform these analyses.

0-subject without confirmed relapses;

\* Select p-value for normal approximation from Wilcoxon Two-Sample Test

## 12.1.1.6 Analysis of Covariance (ANCOVA) for quality of life (QoL) variables

## One sample t-test for quality of life (QoL) variables

The regular one-sample t-test will be used to perform within-group comparisons of continuous (or quantitative) efficacy variables where the normality assumption is held reasonably well. The within-

run;

group analyses for continuous / quantitative variables will compare assessments for the end of treatment vs. baseline within each treatment group. Examples of such analysis include the within group comparisons of the quality of life variable: change from baseline in TSQM total score.

Below is an example of the SAS codes used to perform the analysis. All 3 treatment groups will be used in the model.

```
*************
* * SAS Codes: One sample t-test
* V1 = First timepoint --- e.g.: (baseline);
* V2 = Second timepoint --- e.g.: (post-baseline visit, end of treatment);
* PID = Subject ID or number of observations;
* diff= difference between two timepoints (higher scores indicate better
results);
* NOTE: First, prepare and extract the data for each treatment group.
* Then, in each treatment group, break up the data into the 2 timepoints.
st Ensure that each subject has a value at both timepoints (V1 and V2).
****************
data one;
  input PID V1 V2;
  diff = V2 - V1;
proc ttest data = one sides=u;
  by treat;
  var = diff;
```

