9.5.4 Health related quality of life

Analysis of Treatment Satisfaction Questionnaire for Medication (TSQM v1.4)

The primary analysis for the TSQM will be between group change in Global Satisfaction from baseline to Month 12. Analyses of the Effectiveness, Side Effects, and Convenience domains will also be conducted.

For the TSQM, responses to items are summed and transformed so that higher scores indicate greater satisfaction. Specifically, TSQM scale scores are computed by adding the items loading on each domain. The lowest possible score is subtracted from the composite score and divided by the greatest possible score range. This provides a transformed score between 0 and 1 that is then multiplied by 100. If more than one item is missing from a subscale of the TSQM for a particular patient, this subscale should be considered invalid for that respondent.

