## 7 Health-related Quality of Life (QoL)

## **7.3 TSQM** (Version 1.4)

Treatment Satisfaction Questionnaire for Medication (TSQM) was developed and validated as a general measure for treatment satisfaction. The TSQM version 1.4 modified will be used, which contains 14 items assessing the following 4 domains: Global Satisfaction, Effectiveness, Side Effects, and Convenience. This patient reported outcome (PRO) must be completed prior to any other study visit assessments at the specified visits according to Table 6-1 assessment schedule in study protocol.

Scores for the TSQM version 1.4 will be generated using the authors' scoring algorithm. Missing data will be treated in accordance with the authors' guidelines (Atkinson et al 2004) as follows:

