#### GLOBAL SATISFACTION:

Score =  $\{[(sum of items 12-14) - 3] / 14\} * 100$ 

If only one item is missing:

Item 12 or 13 missing: Score =  $\{[(\text{sum of available items in } 12-14) - 2] / 10\} * 100$ 

Item 14 missing: Score =  $\{[(sum of available items in 12-14) - 2] / 8\} * 100$ 

The higher summary scores indicate better satisfaction with study drug.

Scores for each scale at scheduled visits will be summarized by treatment group with n, mean SD, minimum, Q1, median, Q3, and maximum. The change from baseline score will be compared within treatment group by Wilcoxon signed-rank test (also known simply as the Wilcoxon sign test).

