## 12.1.1.7 Wilcoxon sign test for quality of life (QoL) variables

Wilcoxon signed-rank test (also known simply as the Wilcoxon sign test) can be thought of as the non-parametric equivalent of the regular one-sample t-test. It will be used to perform all within-group comparisons of continuous (or quantitative) efficacy variables. The within-group analyses for continuous / quantitative variables will compare assessments for the end of treatment vs. baseline within each treatment group. Examples of such analysis include the within group comparisons of the quality of life variable: change from baseline in TSQM total score.

Below is an example of the SAS codes used to perform the analysis. All 3 treatment groups will be used in the model.

\*\*\*\*\*\*\*\*\*\*\*\*\*

```
* * SAS Codes: Wilcoxon signed-rank test (or Wilcoxon sign test)
* V1 = First timepoint --- e.g.: (baseline);
* V2 = Second timepoint --- e.g.: (post-baseline visit, end of treatment);
* PID = Subject ID or number of observations;
* diff= difference between two timepoints;
* NOTE: First, prepare and extract the data for each treatment group.
* Then, in each treatment group, break up the data into the 2 timepoints.
* Ensure that each subject has a value at both timepoints (V1 and V2).
**************************
data one;
  input PID V1 V2;
  diff = V2 - V1;
proc univariate data = one;
  by treat;
  var = diff;
run;
```

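### The SAP's example code for the within-arm TSQM t-test is one-sided towards improvement without a stated reason, and it conflicts with the signed-rank test that SAP 7.3 and 12.1.1.7 assign to the same comparison (minor)

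*SAP*

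**What the plan says.** Three places in the SAP deal with within-arm change in TSQM.

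- **Section 12.1.1.6, under the one-sample t-test subheading.** The prose says "The regular one-sample t-test will be used to perform within-group comparisons of continuous (or quantitative) efficacy variables", provided normality holds reasonably well, and gives "change from baseline in TSQM total score" as an example. The sample code computes `diff = V2 - V1` (later minus earlier), carries the comment "diff= difference between two timepoints (higher scores indicate better" (it runs on to the next line), and calls "proc ttest data = one sides=u".
- **Section 7.3, the endpoint's own section.** "The change from baseline score will be compared within treatment group by Wilcoxon signed-rank test". No t-test is mentioned.
- **Section 12.1.1.7.** Of the signed-rank test it says: "It will be used to perform all within-group comparisons of continuous (or quantitative) efficacy variables". It names the same TSQM total score, and its `PROC UNIVARIATE` example sets no one-sided option.

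On the score itself, SAP 7.3 says the instrument "contains 14 items assessing the following 4 domains: Global Satisfaction, Effectiveness, Side Effects, and Convenience" and gives a formula for each domain. Protocol 9.5.4 agrees: "Specifically, TSQM scale scores are computed by adding the items loading on each domain". Neither visible text defines a total score. Protocol 9.5.4 makes the between-group change in Global Satisfaction from baseline to Month 12 the main TSQM analysis.

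**The concern.** The prose promises an ordinary t-test and states no direction, while the code tests only for improvement. `PROC TTEST` is two-sided unless told otherwise, so the option changes the test from what the text describes. The only significance level stated in the plan, for the two primary hypotheses, is two-sided.

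The same within-arm change also has two tests with different tails. The condition for using the t-test is a judgement about normality with no criterion attached, so the choice could be made after seeing the data. A programmer following 12.1.1.6 literally would get p-values that favour improvement and would also have to decide what the total score is.

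TSQM change is a listed secondary objective. What is at stake is the accuracy of the reported within-arm p-values.

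**Working it through.** The documents give no sample size, power or alpha for TSQM, so there is no planned figure to reproduce. The check is what the coded option does to the p-value.

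**Inputs**
- Tail: upper, on later minus earlier, higher is better (SAP 12.1.1.6).
- Illustrative n = 352, the number randomized to fingolimod 0.5 mg (SAP Section 10). The number with paired TSQM data is not given. Using 342 or 370, the other two arms, changes the p-values below by at most about 0.0001.
- Threshold 0.05: an assumption, because no alpha is stated for TSQM.

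**Formulas**, with df = n - 1 = 351:
- Two-sided: p2 = 2 × P(T > |t|)
- As coded: pu = P(T > t)
- Hence pu = p2/2 when t > 0, and pu = 1 - p2/2 > 0.5 when t < 0.

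| t | two-sided p | p as coded |
|---|---|---|
| +1.70 | 0.0900 | 0.0450 |
| +1.80 | 0.0727 | 0.0364 |
| +2.50 | 0.0129 | 0.0064 |
| -1.80 | 0.0727 | 0.9636 |
| -2.50 | 0.0129 | 0.9936 |

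At 0.05 the critical value falls from |t| = 1.967 (two-sided) to t = 1.649 (coded). An improvement with t between these values is significant only under the coded option.

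**Simulation** (20,000 data sets, assumed 250 pairs, normal, SD 1, p read against 0.05):
- No true change: the coded test declared improvement in 5.3% of data sets; the two-sided test did so in that direction in 2.7%. The theoretical values are 5% and 2.5%.
- True fall of 0.3 SD: the coded test was significant in 0%; the two-sided test detected the fall in 99.7%.

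**Does the other planned test see a fall?** In one simulated arm of 352 with a true fall of 0.2 SD, t was -4.30. The coded p was 0.99999, the two-sided t-test p was 0.00002, and the two-sided signed-rank p was 0.0001. The blindness to a fall therefore belongs to the coded t-test and not to the signed-rank test.

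**The score.** Effectiveness, Side Effects, Convenience and Global Satisfaction each have a formula in SAP 7.3. No formula combines them, so the variable named in 12.1.1.6 and 12.1.1.7 cannot be computed from the visible text.

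**The case against.** The best defence is that Section 7.3 governs. It is the endpoint's own section, it names one within-arm test, and 12.1.1.7 supports it. On that reading the t-test would never be run for TSQM.

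The code is also labelled an example and would not run as printed: `var = diff` is not a valid VAR statement, and `by treat` uses a variable that the INPUT line never reads. The SAP's sample code is loose elsewhere too; the primary-model example omits the baseline Gd-lesion covariate that Section 4.2.1 requires. A stray option in such code is weak evidence of a planned one-sided inference. The total score looks like a labelling slip, since 7.3 already summarises each scale. Other quality-of-life text has been removed from the public SAP, which limits what can be inferred about where the template came from.

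Most of this stands, and it sets the severity. It does not remove the inconsistency. The SAP has no rule saying which section prevails, 12.1.1.6 names TSQM explicitly, and Section 12 is headed as the study report's documentation of statistical methods.

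A reader might go further and infer that the plan cannot detect a worsening at all. The documents do not support that: the signed-rank test has no one-sided option, and 7.3 also reports summary statistics for every scale by arm and visit. A reader might also infer an open-ended confidence interval, but 7.3 lists no interval for TSQM change.

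**Conclusion.** The point holds as a minor inconsistency. The example code in 12.1.1.6 contradicts its own prose on sidedness, and the section conflicts with 7.3 and 12.1.1.7 on which test applies.

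The consequence is conditional. If the t-test is run as coded, improvement p-values are exactly halved and every fall gives p above 0.5 on that test. This follows from the definition of the tail and does not depend on n or alpha. The doubling of false claims of improvement, from 2.5% to 5%, additionally assumes that p is read against 0.05.

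The within-arm TSQM tests lie outside the primary testing hierarchy, so the annualized relapse rate result does not change. The between-group Global Satisfaction comparison in Protocol 9.5.4 is also unaffected.

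**What to change.** Either delete the t-test from 12.1.1.6 and keep the signed-rank test of 7.3 as the only within-arm TSQM test, or set `sides=2` and label the t-test as supportive. The first is cleaner because it also removes the undefined normality judgement. In 12.1.1.6 and 12.1.1.7, replace the TSQM total score with the four domain scores, Global Satisfaction first.

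The cost is one code option or a deletion, plus two wording changes. No new data are needed. If the one-sided code would otherwise have been used, some within-arm improvement p-values become less favourable.

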## 12.1.1.7 Wilcoxon sign test for quality of life (QoL) variables

Wilcoxon signed-rank test (also known simply as the Wilcoxon sign test) can be thought of as the non-parametric equivalent of the regular one-sample t-test. It will be used to perform all within-group comparisons of continuous (or quantitative) efficacy variables. The within-group analyses for continuous / quantitative variables will compare assessments for the end of treatment vs. baseline within each treatment group. Examples of such analysis include the within group comparisons of the quality of life variable: change from baseline in TSQM total score.

Below is an example of the SAS codes used to perform the analysis. All 3 treatment groups will be used in the model.

\*\*\*\*\*\*\*\*\*\*\*\*\*

```
* * SAS Codes: Wilcoxon signed-rank test (or Wilcoxon sign test)
* V1 = First timepoint --- e.g.: (baseline);
* V2 = Second timepoint --- e.g.: (post-baseline visit, end of treatment);
* PID = Subject ID or number of observations;
* diff= difference between two timepoints;
* NOTE: First, prepare and extract the data for each treatment group.
* Then, in each treatment group, break up the data into the 2 timepoints.
* Ensure that each subject has a value at both timepoints (V1 and V2).
**************************
data one;
  input PID V1 V2;
  diff = V2 - V1;
proc univariate data = one;
  by treat;
  var = diff;
run;
```

## 12.1.2 Statistical analysis outputs

Results from the primary and secondary efficacy analyses will be presented in Section 16.1.9 of the clinical study report.

The list of outputs that will be generated is provided in RAP Module 7.1.

